#### **D.8.4. Blood pressure.**

**D.8.4.1. Clinic BP.** We will assess clinic BP on two separate occasions, on consecutive days. Every effort will be made to conduct clinic BP measurements at the same time of day with the morning preferred for all participants. At each visit, BP will be measured three times attended and three times unattended using the arm with higher BP during the screening visit. The ordering of approaches will be randomized so that 50% of participants have attended BP measured first and unattended BP measured second at Study Visit 1 and the remaining 50% of participants will have unattended BP measured first followed by attended BP measurements at Study Visit 1. We selected to use the Omron HEM-907XL, rather than the Watch BP Office automated device as it has been used in US studies including a sub-study of NHANES participants and SPRINT. We are not using the BPTru automated BP device as its manufacturer went out of business in September 2017.

**D.8.4.1.1 Attended clinic BP.** For assessment of attended clinic BP, three readings will be obtained from the arm with higher BP during the screening visit, using an appropriate-sized cuff and the Omron HEM-907XL (Omron, Bannockburn, IL, USA), an oscillometric device, by a trained BP technician. The Omron HEM-907XL device has been previously validated against a mercury sphygmomanometer. This device comes with small, regular, large and extra-large cuff sizes and the proper BP cuff size will be determined by measuring the participant's arm circumferences at the mid-point between the acromion and olecranon. Participants will be asked to sit quietly for at least 5 minutes, in a comfortable posture, with feet flat on the floor prior to their BP measurement with the technician in the room. Three BP readings separated by one minute will be obtained with the participant seated with their back supported and their arm positioned at heart level. The BP technician will initiate each reading by pushing the "Start" button on the device. The three BP readings will not be visible to the technician or participant until after the procedure is complete.

**D.8.4.1.2. Unattended clinic BP.** We will obtain unattended clinic BP measurements using the same Omron device used for attended clinic BP measurements (Omron HEM-907XL). It has a memory chip that stores the individual BP readings. The device will be programmed to take three BP readings automatically, spaced one minute apart from the same arm as the attended readings. After positioning the participant, the technician will program the BP device to wait one minute prior to initiating the three readings. The BP technician will then leave the room (i.e., at the start of the one minute resting period). The BP technician will stay outside of the room for 5 minutes to ensure that all three unattended BP measurements are obtained without interruption. To avoid possible reactive effects in the participant, the three BP readings will not be visible to participants.

**D.8.4.2. ABPM and Actigraphy.** ABPM will be performed in the same arm used to measure clinic BP. An appropriate BP cuff size will be selected based on the measurement of each participant's arm circumference. The monitor (SpaceLabs 90227) will be initialized, and the participant fitted with it. The SpaceLabs 90227 monitor has been previously validated and we have used this device in a prior project. The ABPM device will be programmed to take readings every 30 minutes over the 24-hour monitoring period. BP readings on the ABPM will not be visible to participants. Each participant will be instructed to keep his/her arm still and in the neutral position from the time that s/he feels the arm cuff begin to inflate until it is fully deflated. Participants will also be fitted with an Actiwatch activity monitor (Philips Respironics, Bend, OR) on their wrist to wear during the 24-hour ABPM period. Actigraphy will provide estimates of sleep and awake times. The actigraphy data will be merged with the corresponding BP measurements, based on the synchronized time stamps recorded by both devices. Participants will be given a phone number to speak with a staff member if a problem with the monitor occurs. Participants will fill out the ABPM Device Log, which will confirm sleep and awake times.

**D.8.4.3. Sleep HBPM and Actigraphy.** The participant will be given a sleep HBPM device (HEM-7080IC, Omron, Bannockburn, IL, USA) with appropriate-sized cuff and instructed in how to put on the cuff and use the monitor properly. Participants will be instructed to put the HBPM device on the same arm used for all other study procedures, the evening they leave the clinic visit. They will also be fitted with an Actiwatch activity monitor on their wrist to wear during the HBPM period. Participants will be instructed to put on the HBPM device before going to bed and to keep it on until they wake up in the morning (i.e., after 5am). The device will be programmed to take 3 readings, at 2am, 3am, and 4am. Participants will be trained to fill out the HBPM Device Log, which documents sleep and awake times. BP readings on the HBPM will not be visible to participants. One night of sleep HBPM will be conducted.

**D.8.5. Tolerability of ABPM and HBPM.** Tolerability for undergoing ABPM and HBPM will be assessed using a 15-item questionnaire. This questionnaire has items assessing the comfort with wearing the devices and

disturbances resulting from completing ABPM and HBPM. Additionally, there are questions on pain, skin irritation and bruising resulting from wearing the devices. Eight of the questions are answered with a Likert-type scale (e.g., Did you find the monitor interfered with your normal sleeping pattern? With response options of 0 “Not at all”, 5 “Somewhat”, 10 “Extremely”). The remaining 7 questions have response options of “yes” or “no” (e.g., “Did you experience pain from wearing the monitor?”).

**D.8.6. Echocardiogram.** Standard high-quality echocardiograms (M-mode, 2D, and Doppler) will be performed by certified research sonographers at UAB and Columbia University using a Phillips iE33 ultrasound machine. All images will be recorded and stored digitally for offline analysis at the Cardiovascular Physiology Research Laboratory at Columbia (Director, [name]). Cardiac measurements will be obtained according to the 2015 recommendations of the American Society of Echocardiography (ASE) and European Association of Cardiovascular Imaging (EACVI). Left ventricular (LV) measurements for LV end-diastolic dimension (LVEDd), septal wall thickness (SWTd), and posterior wall thickness (PWTd) will be obtained. LVM (grams) will be determined using the ASE formula. LVMI will be calculated as LVM divided by body surface area (g/m^2) and secondarily by dividing by height2.7 (g/m2.7). Left ventricular hypertrophy (LVH) will be examined as an outcome in exploratory analyses, defined as LVMI  $\geq$  96 g/m^2 in females and  $\geq$  116 g/m^2 in males (or LVMI  $\geq$  45 g/m2.7 in females and  $\geq$  49 g/m2.7 in males, when LVM is indexed to height2.7). Per ASE/EACVI guidelines, the method for LV mass estimation and the definition of LVH does not differ by race. **Table 5** shows additional measures.

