### 2. Unattended BP measurements

- a. Explain to participant the steps involved in obtaining unattended BP measurements:
  - i. You will have them turn off their phone and place the phone out of their view but not out of the room
  - ii. Have them sit in a firm chair with a flat back
  - iii. Have them place their feet flat on the floor
  - iv. They should not speak until all three blood pressure readings are obtained
  - v. You will start the blood pressure measurement device
  - vi. You will leave the room for 10 minutes
  - vii. After 5 minutes, they will have their blood pressure measured
  - viii. They will have their blood pressure measured two more times at one minute intervals
  - ix. They should relax but not move or talk until you return to the room
- b. Connect the BP device to the cuff
- c. Position patient for their BP measurement
- d. Start the device for a 5 minute waiting period
- e. Leave the room for 10 minutes

[figure not shown]

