### 3. Attended BP measurements

- d. Explain to participant the steps involved in obtaining unattended BP measurements:
  - i. You will have them turn off their phone and place the phone out of their view but not out of the room
  - ii. Have them sit in a firm chair with a flat back
  - iii. Have them place their feet flat on the floor
  - iv. They should not speak until all three blood pressure readings are obtained
  - v. You will start the blood pressure measurement device
  - vi. After 5 minutes, they will have their blood pressure measured
  - vii. They will have their blood pressure measured two more times at one minute intervals
  - viii. They should relax but not move and there should be no talking until the three blood pressure measurements are taken
- e. Connect the BP device to the cuff
- f. Position patient for their BP measurement
- g. Start the device for a 5 minute waiting period and stay in the room doing other activities without talking to the participant

If the participant asks about his/her clinic blood pressure, the technician should tell the participant that the readings will be given to him/her in a report approximately 7 days following their final study visit if they have provided consent to receive their results.

A standard automated blood pressure measurement monitor (Microlife WatchBP Office AFIB) and a specific protocol for the measurement of blood pressure will be utilized.

[figure not shown]

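### The research plan and the manual specify different clinic BP procedures, and under the research plan's rule rest time and triggering would be tied to attendance in the primary Aim 1 contrast

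*Combined protocol and SAP*

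**What the plan says.** **Research plan, attended BP (D.8.4.1.1).** "Participants will be asked to sit quietly for at least 5 minutes", with the technician in the room. On triggering: "The BP technician will initiate each reading by pushing" the Start button.

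**Research plan, unattended BP (D.8.4.1.2).** "The device will be programmed to take three BP readings automatically, spaced one minute apart", and before that "the technician will program the BP device to wait one minute prior to initiating the three readings". The technician leaves at the start of that minute and stays out for 5 minutes. No other rest is described.

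**Research plan, device (D.8.4.1).** "We selected to use the Omron HEM-907XL, rather than the Watch BP Office automated device".

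**Manual of Operations, Clinic BP Measurements.** The unattended instruction is "Start the device for a 5 minute waiting period", followed by 10 minutes out of the room. The attended instruction sets the same 5-minute wait, with the technician staying in the room without talking. The initializing procedures for the clinic device set 300 seconds of rest, 60 seconds between readings and three consecutive readings for either method. The Visit 1 and Visit 2 data collection forms repeat the 5-minute wait for both. The device is described as "A standard automated blood pressure measurement monitor (Microlife WatchBP Office AFIB").

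**Analysis (D.11.4).** The primary Aim 1 analyses use the first three clinic readings at each of Visits 1 and 2; readings four to six are for sensitivity analysis. The order of methods at Visit 2 is the reverse of Visit 1.

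**The concern.** Aim 1 asks whether unattended measurement estimates awake ambulatory BP better than attended measurement does. A reader will attribute any difference to the observer's absence. That is safe only if the two conditions are otherwise alike. In the research plan they differ in three ways: presence of the technician, rest before the first reading, and how readings are started. The last two would feed into the attended-unattended comparison and into each method's distance from awake BP, and so into Hypotheses 1a, 1b and 3a.

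The research plan holds earlier work to this standard. Its Table 2 of limitations (item 2) faults prior studies because the way attended BP was taken could itself explain the difference from unattended BP. Section C presents use of the same oscillometric device for both methods as an innovation.

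**Working it through.** The documents state no figure for this point that could be reproduced, so the check compares the texts and follows the consequence through the design.

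**1. The two specifications side by side**

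| | Research plan, attended | Research plan, unattended | Manual, attended | Manual, unattended |
|---|---|---|---|---|
| Rest before first reading | at least 5 min | 1 min | 5 min | 5 min |
| Interval | 1 min | 1 min | 1 min | 1 min |
| Trigger | technician, each reading | automatic | automatic | automatic |
| Technician | present | out 5 min | present | out 10 min |
| Device | Omron HEM-907XL | same Omron | WatchBP Office AFIB | same WatchBP |

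Rest difference between conditions: research plan, at least 5 − 1 = 4 minutes; manual, 5 − 5 = 0.

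**2. Is the one minute a slip?** Minimum session time is rest plus two 1-minute intervals, leaving out inflation time.
- Research plan: 1 + 2 = 3 minutes, which fits 5 minutes out of the room. A 5-minute rest would need 5 + 2 = 7 minutes, which does not fit.
- Manual: 5 + 2 = 7 minutes, which fits 10 minutes out of the room.

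Each text is coherent on its own terms. They are two different procedures, and the one minute is not a typing error.

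**3. Does randomised order remove the difference?** The primary analysis takes the first set at each visit, and the order reverses at Visit 2. Each participant therefore contributes one first-placed attended set and one first-placed unattended set. Let α be the effect of attendance and ρ the combined effect on unattended BP of shorter rest and automatic triggering. Then

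attended − unattended = α − ρ under the research plan (ρ unknown), and α under the manual (ρ = 0).

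Day and order effects balance across the two randomised orders. The term ρ is the same in both orders, so it does not cancel. The covariates in D.11.2 and the mixed model with randomisation assignment in D.11.4.1 do not include rest, trigger or device. In the sensitivity analysis, a second-placed unattended set follows the attended rest and readings, so the imbalance is smaller there.

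**4. What the reported comparison contains.** The results Table 2 of the analysis plan gives attended minus unattended systolic BP as 0.69 mm Hg (95% CI 0.39 to 0.99).
- If visits followed the manual, 0.69 contains no ρ.
- If visits followed the research plan, 0.69 already contains it. On first-placed sets alone, α would be 0.69 + ρ.

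The table does not appear to use first-placed sets alone. Its extremes include 92.2, 179.5, 90.5 and 179.8. With whole-number readings, a mean of three ends in .0, .3 or .7; a mean of six can also end in .2, .5 or .8. These values fit means of six, as the Results Packet describes. Each method's mean would then pool a first-placed and a second-placed set, and a full ρ would not apply to both.

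**The case against.** The strongest answer is that the research plan is a funding application and was superseded. D.2 requests funding and sets aside the first six months to finalise the protocol. The manual has COVID-19 procedures, device screens and visit forms, and it replaces all three BP devices: clinic (Omron to WatchBP Office AFIB), ambulatory (SpaceLabs to WatchBP O3) and home (Omron to WatchBP Home N). On that reading equal rest was already in place. This is plausible and is the main limit on the point. It is still an inference, because no passage gives the manual precedence.

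A second answer is that Aim 1 compares procedures as used, not presence alone; section B.6.1.1 describes unattended devices as running after about a minute of rest. A package comparison can be defended. It would then have to be declared as one, and it sits badly with the research plan's own criticism of earlier studies.

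A reader might also infer that Columbia followed the research plan and UAB the manual, so that the pooled result mixes two procedures on two devices. The documents do not show this. The manual's clinic instructions are written for UAB, but its site list names both centres, and its telephone script describes enrolling 660 adults with visits at the UAB clinic. No passage shows any participant measured under the one-minute rule or on an Omron device. Mixed use is a possibility only.

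**Conclusion.** The conflict is in the text and is unresolved. If the research plan's rule were applied, rest time and triggering would be tied to attendance in the primary Aim 1 contrast, and randomised order would not separate them. If the manual was followed at every visit, this confounding is absent and the reported tables are unaffected by it.

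No size can be given, because the documents contain no estimate of how rest or triggering affects BP. A reader might infer that a modest rest effect would wipe out or reverse the reported 0.69 mm Hg. That does not follow: the figure either carries no such bias or already includes it. If shorter rest raised unattended BP, correction would enlarge the difference. Nor are the 1.2 and 1.5 mm Hg in D.12.1.1 a suitable yardstick, since they concern a difference between absolute distances from awake BP, not the attended-unattended mean difference.

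The conclusion rests on reading D.8.4.1.1 and D.8.4.1.2 as written and on the primary data set defined in D.11.4. It takes no view on which rest period is the better one.

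**What to change.** Reconcile the passages so that D.8.4.1.1 and D.8.4.1.2 carry one clinic BP specification: the same device, rest, interval and triggering for both conditions, as the manual already has, with technician presence the only difference. Name the device and state that the specification applies at both sites.

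State which procedure was used at the visits. If all followed the manual, the correction is one of wording. If any participants were measured under the unequal-rest rule or on the other device, flag them and report the results Table 2 with and without them.

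The cost is about 5 − 1 = 4 more minutes per unattended session than the research plan describes. Against the manual there is no added time.

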**Table 5. Additional echocardiographic measures.**

**LV diastolic function:** E/A ratio, E' (m/s), A' (m/s), E/E' ratio, isovolumetric relaxation time (ms), deceleration time, ms

**LV systolic function** defined by LV ejection fraction (LVEF, %) =  $100 \times (LVEDV - LVESV) / LVEDV$ .

**Other parameters:** Shortening (FS, %); left atrial dimension (cm) and volume (cm^2).

**Hemodynamics:** stroke volume (SV, mL) = VTI x cross-sectional areaLVOT; heart rate (HR); cardiac output (L/min) = SV x HR.

**D.8.7. Albuminuria.** The urine sample collected during the first visit will be used for the measurement of creatinine and albumin. Consistent with prior research, urinary albumin excretion rate will be calculated using the formula: urinary albumin in milligrams per liter / (k \* urinary creatinine in grams per liter) (denoted A/kC), where k adjusts for race and sex differences in typical daily creatinine excretion. Urinary creatinine concentration in men will be multiplied by 0.68 and by 0.88 for African Americans. This approach will allow the use of 25 mg/g as the A/kC cut-point for microalbuminuria regardless of a participant’s race and sex.

**D.9. Staff training.** Prior to initiation of recruitment, Drs. [name], [name], [name], and [name] will conduct centralized training of study staff from each site in the conduct of all study measures including clinic-measured BP, ABPM, HBPM, and echocardiography. Once data collection begins, they will monitor data collection and confirm that the study protocol is being followed. Annual centralized re-training will be conducted.

**D.10. Data management.** The Pharmacoepidemiology and Economics Research (PEER) Unit ([name] – co-director) at UAB will provide coordination and logistical support for all aspects of the proposed study. The PEER Unit has 3 program coordinators, 2 systems analysts/programmers, 15 PhD and Master’s level statisticians and 4 research associates with experience designing data collection systems and analyzing data, including ABPM, from epidemiology studies.

**D.10.1. Study database.** Data collection for this study will occur electronically through a system and website developed in RedCap by [name], a programmer in the UAB PEER Unit. RedCap provides a secure, password protected, web application that will be accessible to staff at UAB and Columbia University. For the current study, our programmer will develop an online database for randomizing participants and electronic web-based forms for conducting data collection. The RedCap platform is HIPAA compliant and we have used RedCap in prior studies of ABPM. Data collection through RedCap will be converted to SAS Version 9.4.

#### **D.10.2. Data transfer.**

**D.10.2.1. ABPM, sleep HBPM, actigraphy, and Device Logs.** Upon return of the ABPM, HBPM, actigraph, and Device Logs, data will be downloaded to a computer and then backed up to a secure network server. Data will be transferred daily to the PEER Unit at UAB using DatAnywhere, a HIPAA compliant file transfer protocol that we used in our AHA-SFRN study. Monthly reports that track data quality will be generated. If data issues are identified (e.g., frequent ABPM or HBPM reading errors), staff will be re-trained.

**D.10.2.2. Echocardiographic measures.** The echocardiographic studies (with unique study identifiers; i.e. de-identified) will be saved to DVD/CD, and backed up to secure research servers at each site. The studies at UAB will be sent to the Cardiovascular Physiology Research Laboratory at Columbia for analysis.

**D.10.3. Data management and cleaning.** All data cleaning will be managed by a statistician at the UAB PEER Unit supervised by [name]. A uniform data editing algorithm, established by Drs. [name] and [name] and used in prior studies, will be implemented to confirm acceptability of the ABPM data and exclude extreme outliers. Minimal editing is the general rule; less than 0.1% of readings are typically excluded. The awake and sleep periods on ABPM will be defined by the actigraphy recording, complimented by self-report

awake and sleep periods from the Device Log. For sleep BP on HBPM, we will confirm that participants were asleep when the the BP readings were obtained using actigraphy data and the HBPM Device Log.

**D.10.4. Minimum number of BP readings required on ABPM and HBPM.** No consensus exists on the number of readings required to consider an ABPM recording complete. Consistent with our prior studies, we will require 14+ awake BP readings, and 5+ sleep BP readings, and  $\geq 80\%$  of the planned 48 readings (39+ total valid readings). We will require three SBP and DBP readings for a sleep HBPM recording to be complete. We will continue recruitment until 600 participants have complete ABPM and sleep HBPM readings.

**D.10.5. Phenotypic measures on ABPM and HBPM.** Awake and sleep BP values will be computed using the average of all BP readings from the awake and sleep periods, respectively. In addition to studying mean BP levels, we will calculate three BP phenotypes: white coat hypertension, masked hypertension, and nocturnal hypertension (Table 6). Unattended clinic BP thresholds are based on the Canadian guidelines.

**Table 6. Phenotypes to be evaluated in the proposed study.**

Phenotype	Attended clinic SBP/DBP	Unattended clinic SBP/DBP	Out-of-clinic SBP/DBP
White coat Hypertension	$\geq 140/90$ mm Hg	$\geq 135/85$ mm Hg	Awake $< 135/85$ mm Hg
Masked Hypertension	$< 140/90$ mm Hg	$< 135/85$ mm Hg	Awake $\geq 135/85$ mm Hg
Nocturnal Hypertension	Not applicable	Not applicable	Sleep $\geq 120/70$ mm Hg

**D.11. Statistical analysis.** All data will be analyzed by a statistician blinded to participants' randomization assignments and a code (e.g., 0 or 1) will be used to represent different randomization assignments.

Assignments will be unmasked after completion of the statistical analyses. The distribution of each BP measure, covariate, and echocardiographic measure will be calculated. Variables will be explored for outliers and when identified the staff in the field sites will be asked to investigate them further.

**D.11.1 Missing data.** Missingness in our prior studies has been uncommon. Our primary approach to missing data is to collect complete data. We will examine missing data and use multiple imputation, as appropriate.

**D.11.2 Multivariable adjustment.** Several analyses will include multivariable adjustment. Multivariable adjustment will be guided by biologic plausibility and will be contingent on the specific hypothesis being tested. In general, we plan two levels of adjustment. An initial model will include adjustment for age, race/ethnicity, sex and clinic site (UAB or Columbia). A second model will include additional adjustment for education, body mass index, smoking, physical activity, alcohol consumption, stress, anxiety, outdoor temperature, sleep quality, diabetes, eGFR, and 10-year predicted CVD risk. Co-linearity will be assessed using variable inflation factors.

**D.11.3. Exploratory statistics comparing unattended and attended BP.** We will calculate characteristics of participants by randomization assignment: unattended then attended clinic BP measurement or attended then unattended clinic BP measurement at the first visit. Scatterplots will be assembled to show the relationship between unattended clinic BP versus awake BP and attended clinic BP versus awake BP. For each comparison, intraclass correlation coefficients will be calculated. The statistical significance of the difference in the correlation coefficients will be calculated using the Fisher r-to-z transformation accounting for the correlation between attended and unattended clinic BP. We will also assemble Bland-Altman plots showing the differences between unattended and attended BP, separately, versus awake BP on ABPM.

**D.11.4. Aim 1. Test whether measuring unattended clinic BP with an automated device will provide a more accurate estimate of awake BP on ABPM than measuring attended clinic BP with an automated device.** Our primary analyses for Hypothesis 1 will be tested using the first three clinic BP measurements obtained at Visits 1 and 2. In sensitivity analyses, we will use the fourth through sixth BP measurements from these visits. Separate analyses will be performed for SBP and DBP.

**D.11.4.1. Hypothesis 1a: The absolute difference with awake BP will be smaller for unattended vs. attended clinic BP.** The absolute difference between mean unattended clinic BP and awake BP and mean attended clinic BP and awake BP, separately, will be calculated. We will test whether these differences are statistically significantly different from zero using paired t-tests. Next, we will determine whether the absolute difference between unattended clinic BP and awake BP is smaller than the absolute difference between attended clinic BP and awake BP by calculating if the difference in differences (i.e., absolute difference between unattended clinic BP and awake BP minus the absolute difference between attended clinic BP and awake BP) is less than zero using a paired t-test. If the absolute differences between unattended and attended clinic BP and awake BP differs by randomization assignment, we will use a mixed model with randomization assignment as a covariate. This analysis will be performed in the overall population and in sub-groups defined by age (categorized in tertiles), race/ethnicity (white, African American, Hispanic) and sex.

**D.11.4.2. Hypothesis 1b: The agreement between hypertension in the clinic and awake hypertension will be higher for unattended versus attended clinic BP.** Also, the prevalence of both white coat and masked hypertension will be lower when BP is measured unattended versus when it is measured

**attended in the clinic.** Using the first three clinic BP measurements obtained at each visit and awake BP from ABPM, we will calculate the prevalence of clinic hypertension, based on unattended and attended measurements separately, and awake hypertension. We will calculate overall agreement and agreement above that expected by chance alone (i.e., the Kappa statistic) between (1) clinic hypertension, measured attended, and awake hypertension and (2) clinic hypertension, measured unattended, and awake hypertension. We will calculate the prevalence of white coat hypertension and masked hypertension defined using unattended and attended clinic BP, separately, and awake BP from ABPM. The statistical significance of the differences in these statistics when BP is measured unattended versus attended will be calculated using McNemar tests and bootstrapping techniques as these measures are not independent.

**D.11.5. Aim 2. Test whether a new HBPM device provides an accurate approach for measuring sleep BP.** We will calculate the characteristics of participants randomized to have their sleep BP measured by (1) ABPM then HBPM or (2) HBPM then ABPM. The statistical significance of differences across the randomization assignments will be calculated using t-tests and chi-square tests, as appropriate.

